- Death occurs that is considered possibly, or definitely related to vaccination
- A life-threatening reaction occurs that is considered possibly, probably, or definitely related to vaccination
- Occurrence of a SUSAR
- Occurrence of an acute allergic reaction or anaphylactic shock following the administration of vaccine investigational product

If any one of the following halting rules are met, challenge of participants will be suspended until after a review of safety data by the IDMC. Other study activities for safety and immune responses will continue during IDMC review. The IDMC will recommend that the study continues as planned, stops, or resumes with modification.

Occurrence in any participant of:

- A reduction of peak expiratory flow (PEF) below 50% of the baseline value, or moderate or severe lower respiratory symptoms occurring within 14 days of challenge
- Pulse oximetry that on repeat monitoring over one hour falls below a value of 90%
- Grade 3 or 4 AE or clinical laboratory abnormality considered related to the challenge agent AND of concern to the Investigator or Medical Monitor. Grade 3 headache or fatigue which resolves within 24 hours will not be a reason for halting unless of concern to the Investigator or Medical Monitor.
- More than three cases of influenza that are sufficiently severe to warrant antiviral therapy
- Laryngospasm, bronchospasm, or anaphylaxis associated with the study drug or challenge within 72 hours of study drug or challenge administration
- Any SAE for which causality is either unknown or related to challenge
- Any case of suspected myocarditis
- Any death

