9.1.3 Safety Data

Safety parameters will be tabulated and analysed descriptively.

Adverse Events

The original terms used in the eSource documents by Investigators to identify AEs will be fully described and coded according to the Medical Dictionary for Regulatory Activities (MedDRA).

The reported AEs will be allocated to phases based on their start date. All AEs will be listed. All AEs with onset after Day 1 of vaccination will be summarized by treatment group. Summaries, listings, and narratives may be provided, as appropriate. Summaries will include at a minimum SAEs, and for both solicited and unsolicited AEs, the severe (grade 3+ events), related AEs, and AEs following challenge.

Clinical Laboratory Tests

Each continuous biochemistry and haematology laboratory test will be evaluated by means of descriptive statistics (i.e., number of participants, mean, SD, median, minimum, and maximum) on the actual values, at each assessment time point and by vaccination group.

Relative changes in clinical laboratory test values compared to values at baseline will be evaluated according to the appended toxicity scale or in accordance with the normal ranges of the clinical laboratory (below, within, or above normal range) for parameters for which no toxicity grades are defined.

A listing of participants with any clinical laboratory test result outside the reference ranges will be provided.

Vital Signs

Pulse rate, temperature, SBP, and DBP will be evaluated by means of descriptive statistics (actual values and changes from Day 1 to Day 2 of the vaccine phase and from Day 1 of the challenge phase and frequency tabulations at each assessment time point and by vaccination group).

Pulse oximetry will be measured during the entire challenge phase.

The percentage of participants with values beyond clinically important limits (as defined in the Toxicity Tables) will be summarized.

Electrocardiogram

ECG variables will be evaluated by means of descriptive analysis by the Investigator at each assessment time point.

The percentage of participants with ECG abnormalities will be summarized.

The ECG variables that will be analysed by electronic capture from the ECG include heart rate, PR interval, QRS interval, QT interval.

Physical Examination

Abnormal findings in physical examination will be listed.

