3.3 VITAL SIGNS

3.3.1 Available data

The following vital signs parameters are collected: pulse rate, systolic (SBP) and diastolic blood pressure (DBP) in supine position, body temperature, oxygen saturation.

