3.3.2 Derivation rules

Abnormalities are defined in below table.

Vital sign	Pulse rate (bpm)		SBP (mmHg)		DBP (mmHg)	Temp (°C)
Abnormality	Tachy cardia	Brady cardia	Hyper tension	Hypo tension	Hyper tension	Fever
Normal	55-100	55-100	90-140	90-140	≤ 90	
Grade 1	101-115	50-54	141-150	85-89	91-95	38.0-38.4
Grade 2	116-130	45-49	151-155	80-84	96-100	38.5-38.9
Grade 3	> 130	< 45	> 155	< 80	> 100	39.0-40.0
Grade 4						> 40.0

	Statistical Analysis Plan	
FLU010	Final analysis	Final 3.0 of 15JUN2020

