3.3.3 Presentation of results

All tables will be presented by analysis phase (vaccination / challenge). Analysis phases are defined in section 5.2.1.

Vital signs parameters will be summarised by means of descriptive statistics at each analysis visit. Actual values and changes from baseline will be tabulated separately.

Abnormalities will be presented as cross-tabulations of the abnormality at each post-baseline analysis visit versus the baseline abnormality and as cross-tabulations of the worst-case abnormality versus the baseline abnormality. Numbers of subjects with treatment-emergent abnormalities will also be shown.

All vital signs data will be listed, but only for subjects with any post-baseline abnormality or clinical significant value.

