For vaccination and challenge assessments on or after their respective reference datetime, the analysis will use the visits and time points indicated on the subject's case report form (CRF). Unscheduled assessments on or after the reference datetime will only be listed.

The screening value is the last available and non-missing value before vaccination. Reason for this approach is the use of retest results for subject eligibility assessment.

5.2.5 *Worst-case*

A worst-case analysis visit will be created for parameters for which abnormalities and/or toxicity grades are defined to summarise values considered as the worst-case. For abnormalities it is derived per parameter and in case both the lowest and the highest values are considered abnormal, a subject can have two worst-case analysis visits for a same parameter within each phase. For toxicity grades the worst-case is the value associated to the highest toxicity grade and is derived per parameter and toxicity direction (low / high).

Worst-case will be derived within each post-screening phase, including unscheduled assessments.

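### The SAP sets no oxygen-saturation category, so no vital-signs table counts by arm the participants below the protocol's 90% halting value

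*SAP*

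**What the plan says.** Protocol 8.3 gives, among the events that halt challenge when seen in any one participant: "Pulse oximetry that on repeat monitoring over one hour falls below a value of 90" per cent. Challenge then stops until the IDMC has reviewed safety. Protocol 7.2.4 counts pulse oximetry as a vital sign, and protocol 9.1.3 adds: "Pulse oximetry will be measured during the entire challenge phase".

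SAP 3.3.1 lists the vital signs available for analysis as "pulse rate, systolic (SBP) and diastolic blood pressure (DBP) in supine position, body temperature, oxygen saturation". SAP 3.3.2 then states "Abnormalities are defined in below table". That table has columns for tachycardia, bradycardia, systolic hypertension and hypotension, diastolic hypertension, and fever. It has none for saturation.

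Three other SAP rules decide what happens to a saturation value:

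- Section 5.2.4, on visits: "Unscheduled assessments on or after the reference datetime will only be listed".
- Section 5.2.5, on the worst case: "A worst-case analysis visit will be created for parameters for which abnormalities and/or toxicity grades are defined". Unscheduled readings feed this derivation.
- Section 3.3.3, on listings: "All vital signs data will be listed, but only for subjects with any post-baseline abnormality or clinical significant value".

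**The concern.** The sponsor considers a saturation below 90% serious enough to stop challenge, but the analysis plan gives it no category. Protocol 7.2.1 acknowledges that priming influenza-specific T cells could in theory make illness after challenge worse. Saturation is an objective measurement bearing on that question, taken under blinded conditions in both arms. A by-arm count of participants below the halting value is what a safety reader would look for, and none of the planned vital-signs tables provides it. The readings that confirm a fall are also the ones most likely to be unscheduled, and the SAP's by-visit tables leave unscheduled readings out.

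**Working it through.** No arithmetic applies, because the question is which output a reading reaches. I traced an illustrative challenge-phase reading of 88% through each planned route.

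**Inputs.** The halting limit is below 90% (protocol 8.3). Saturation is collected (SAP 3.3.1) and has no abnormality definition (SAP 3.3.2). Protocol Appendix 2 has no saturation grade either. Pulse oximetry is marked once per day from Day -1 to Day 10 in the Period 2 schedule, with no time point for repeats.

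| Output | 88% at a scheduled time | 88% on an unscheduled repeat |
|---|---|---|
| By-visit descriptives, by arm (SAP 3.3.3, 5.4.1, 5.4.3) | Included; visible at most as the minimum | Not included (5.2.4) |
| Cross-tabulation and treatment-emergent count, table 14.3.3.3 | None: no category | None: no category |
| Worst-case visit (5.2.5) | None: parameter not eligible | None: parameter not eligible |
| Listing 16.2.9.1 (3.3.3) | Only with a clinically-significant flag, or another defined vital-sign abnormality in that participant | Same condition |
| Adverse event tables (protocol 7.2.4, SAP 3.1.3) | If the investigator records an event | If the investigator records an event |

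**Scheduled readings.** A minimum of 88% shows that at least one participant was that low at that visit. It does not say how many participants were below 90%, or whether the same person was low at several visits.

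**Repeat readings.** A participant with 97% at the scheduled time and 88% on repeats contributes 97% to the descriptives and nothing to any vital-signs count. This assumes that repeats within the hour are stored as unscheduled assessments. The documents do not say so, but the schedule offers no other slot for them.

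**The listing.** Section 5.2.4 sends unscheduled readings to the listing, and section 3.3.3 restricts the listing to certain participants. A saturation of 88% does not itself meet that restriction.

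**Adverse events.** Entry depends on the investigator finding the change clinically relevant. Protocol 10.6 also prefers a diagnosis over its component signs, so a desaturation could be coded under a respiratory or influenza term and not be identifiable as low saturation.

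**The case against.** A reader might infer that a desaturation enters no by-arm table at all. The documents do not support that. A scheduled low value is in the by-arm descriptives. A change judged clinically relevant is recorded as an adverse event and counted by arm, phase and preferred term. An investigator is unlikely to call a sustained fall that stops challenge irrelevant.

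A reader might also infer that a low value is listed only if someone flags it. That is too strong as well. The listing rule works per participant, so a fever, a fast pulse or a raised blood pressure brings in all that participant's vital signs. Someone ill enough to desaturate may well have one of these, though the documents give no rate.

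Nor does the SAP contradict the protocol. Protocol 9.1.3 ties the summary of out-of-limit values to the toxicity tables, which have no saturation entry. Section 8.3 is a rule of conduct with its own safeguard in the IDMC, and nothing requires a halting value to become an analysis category. Worsening illness is also compared through viral load, symptom scores, solicited symptoms and lung function. The phrase in 8.3 about repeat monitoring suggests that a low reading came first. If that reading was scheduled, it is in the descriptives.

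All of this stands and narrows the point, but it does not supply the missing count. A minimum is not a number of participants, the adverse event and flag routes rest on judgement, and IDMC review is not a table in the final analysis. Absence from Appendix 2 is no obstacle: SAP 3.4.2 already sets ECG categories that the appendix lacks.

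**Conclusion.** The gap is real and limited. SAP 3.3.2 defines no saturation abnormality, so no planned vital-signs table counts by arm the participants below the protocol's halting value. Scheduled low readings appear only within by-visit descriptives. Unscheduled repeats reach the outputs only through an adverse event entry, a clinically-significant flag, or another abnormality in the same participant.

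The size cannot be estimated: the documents give no desaturation rate, and the number of participants is likely small. A reader might offer the upper limit for zero events among 80 challenged vaccine recipients, 1 − 0.05^(1/80) = 3.7% (one-sided 95%). That is the precision of any zero count in 80 people and does not measure how many readings the plan would miss.

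The conclusion about repeat readings rests on their being stored as unscheduled. The conclusion about the missing count does not depend on this. Efficacy analyses are unaffected. This is an inexpensive improvement to safety reporting, not the correction of a contradiction.

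**What to change.** In SAP 3.3.2, add for the challenge phase an oxygen-saturation category at the limit already in protocol 8.3 (below 90%), and label the remainder simply as not below that limit. Existing rules then do the rest: section 5.2.5 derives a worst case with unscheduled readings included, table 14.3.3.3 shows the result by arm, and a reading below the limit triggers listing 16.2.9.1. State explicitly that number and percentage of participants are shown for each arm.

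A footnote should say that the count is of participants with any reading below 90%, which is broader than the halting event in 8.3 because that requires repeat monitoring. Isolated artefactual readings may therefore be counted; the listing lets a reader see them.

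The cost is one category in an existing table, with no new data. The count complements the adverse event tables and IDMC review, changes reporting only, and proposes no new clinical limit.

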3.3.3 Presentation of results

All tables will be presented by analysis phase (vaccination / challenge). Analysis phases are defined in section 5.2.1.

Vital signs parameters will be summarised by means of descriptive statistics at each analysis visit. Actual values and changes from baseline will be tabulated separately.

Abnormalities will be presented as cross-tabulations of the abnormality at each post-baseline analysis visit versus the baseline abnormality and as cross-tabulations of the worst-case abnormality versus the baseline abnormality. Numbers of subjects with treatment-emergent abnormalities will also be shown.

All vital signs data will be listed, but only for subjects with any post-baseline abnormality or clinical significant value.

3.4 ELECTROCARDIOGRAMS

3.4.1 Available data

The following electrocardiogram (ECG) parameters will be collected: heart rate (HR), QRS interval, PR interval, QT interval and corrected QT interval (Fridericia).

3.4.2 Derivation rules

Abnormalities for HR, QRS and PR interval are defined in below table.

	HR (bpm)	PR (ms)	QRS (ms)
Low	< 40	< 110	-
Normal	40-100	110-220	≤ 120
High	> 100	> 220	> 120

Note: For the worst-case analysis visit, as defined in section 5.2.5, an additional category low + high is defined in case there are both low and high values within the same phase.

For QTc interval (ms), the following categories are defined:

- Actual values:
 - ≤ 450 (normal)
 -]450; 480]
 -]480; 500]
 - > 500
- Changes:
 - ≤ 30 (normal)
 -]30; 60]
 - > 60

Note: The worst-case, as defined in section 5.2.5, is the highest value and associated change.

	Statistical Analysis Plan	
FLU010	Final analysis	Final 3.0 of 15JUN2020

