challenge studies. Nevertheless, because the challenge agent is wild-type (although a seasonal strain which may be further passage-attenuated), it is possible that infrequent or rare clinically significant events may occur. A number of serious events have been associated with community-acquired Influenza infection [24]. Most were seen to occur primarily during pregnancy or in elderly individuals and those with chronic underlying medical conditions. Such events have been more frequently observed during pandemic years and have included pulmonary complications (including primary viral pneumonia, secondary bacterial pneumonia, and exacerbations of underlying chronic obstructive pulmonary disease, and asthma), along with worsening of underlying cardiac conditions such as congestive heart failure and ischemic heart disease. Much less frequent (and generally rare) complications have also been reported, including myositis, rhabdomyolysis, and neurologic complications such as encephalopathy (Reye's syndrome), encephalomyelitis, transverse myelitis, aseptic meningitis, focal neurologic disorders, and Guillain-Barré syndrome. The occurrence of Reye's syndrome has been reported predominately in children less than 14 years of age (90% of cases reported were in this age group) and the incidence has dramatically declined during the past 2 decades from a peak of 500 cases per year in the 1970s. This decline is thought to be related to the understanding of the role of salicylates in Reye's syndrome. Pericarditis and myocarditis have been noted in adults, along with electrocardiographic (ECG) abnormalities in up to 53% of infected adults, typically with no cardiac symptoms [25, 26]. However, most of these ECG abnormalities resolved within 28 days, and did not result in detectable myocardial damage (as measured by creatine kinase isoenzyme MB or troponin I levels) or reduced ejection fractions.

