Vital sign parameters will be assessed after 5 minutes in supine position at the time points indicated in the Time and Events Schedule. The vital sign parameters that will be assessed are temperature, supine systolic and diastolic blood pressure (SBP and DBP, respectively), pulse rate, and pulse oximetry.

These parameters will be measured using a completely automated device consisting of an inflatable cuff and an oscillatory detection system. All values will be registered on a built-in recorder so that measurements are observer-independent.

Any change from baseline in vital sign values occurring during the study that is considered to be clinically relevant by the Investigator should be recorded in the AE section of the eSource system.

7.2.5 *Spirometry*

Spirometry is to be performed on Day -1 prior to challenge and on Day 10 post-challenge. This assessment may be performed during an Unscheduled Visit at the discretion of the Investigator.

7.2.6 *Electrocardiogram*

Digital twelve-lead ECGs will be recorded in supine position at the time points indicated in the Time and Events Schedule.

The interpretations of the ECGs will be performed and recorded by the Investigator or his/her designee at the clinical site. Any change from baseline/pre-vaccination ECG occurring during the study that is considered to be clinically relevant by the Investigator should be recorded in the AE section of the eSource system. Specifically, the qualified reader will look for signs of myocarditis, which include non-specific ST-segment and

T-wave abnormalities, sinus tachycardia and conduction abnormalities, such as bundle-branch blocks or atrioventricular conduction delays.

7.2.7 *Physical Examination*

Physical examination or symptom-directed examination will be performed at the time points indicated in the Time and Events Schedule.

Physical examination at screening will include height and weight. To obtain the actual body weight, participants must be weighed at screening 2 while lightly clothed. The height should be measured barefoot.

Any change in physical examination occurring during the study that is considered to be clinically relevant by the Investigator should be recorded in the AE section of the eSource system.

7.2.8 *Other Assessments*

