16.2.10.1 ECG Results for Subjects with Abnormal Values SAF

16.2.10.2 ECG Interpretation and Morphology for Subjects with any Abnormal Interpretation SAF

LUNG FUNCTION

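### The SAP's ECG tables count only heart-rate and interval cut-offs, so ST-segment and T-wave changes not recorded as adverse events are listed but left out of the percentage with ECG abnormalities that the protocol says will be summarised

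*SAP*

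**What the plan says.** Protocol 7.2.6 is specific about what is sought on the ECG. It says that "the qualified reader will look for signs of myocarditis, which include non-specific ST-segment and", and the sentence then runs on to the remaining signs: "T-wave abnormalities, sinus tachycardia and conduction abnormalities, such as bundle-branch blocks or atrioventricular conduction delays". The same section, and footnote 6 to the challenge schedule, send any change that the investigator considers clinically relevant or significant to the adverse event record.

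Protocol 9.1.3 makes a general reporting commitment: "The percentage of participants with ECG abnormalities will be summarized". Its next sentence names the machine-read variables: "The ECG variables that will be analysed by electronic capture from the ECG include heart rate, PR interval, QRS interval, QT interval".

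SAP 3.4.1 describes the data as follows: "The following electrocardiogram (ECG) parameters will be collected: heart rate (HR), QRS interval, PR interval, QT interval and corrected QT interval (Fridericia"). Interpretation and morphology are not mentioned there. In SAP 3.4.2, "Abnormalities for HR, QRS and PR interval are defined in below table", followed by categories for QTc values and changes. SAP 3.4.3 cross-tabulates these categories against baseline. SAP 8.1 lists four ECG tables: descriptive statistics of values (14.3.4.1) and of changes (14.3.4.2), abnormalities versus baseline (14.3.4.3), and QTc change categories (14.3.4.4).

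The reader's findings appear once, as listing 16.2.10.2 in SAP 8.2: "ECG Interpretation and Morphology for Subjects with any Abnormal Interpretation". SAP 6.1 records no change to the planned analysis.

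**The concern.** The protocol directs the reader to a class of finding that the SAP's ECG tables have no category for. A participant with a new ST-T change and unremarkable intervals contributes only normal categories to the ECG tables, and the change itself is seen only in a listing unless it becomes an adverse event.

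This matters because cardiac safety after challenge is a stated interest. Myocarditis is an adverse event of special interest (protocol Appendix 1), and any suspected case suspends challenge (8.3). Protocol 7.2.1 raises a theoretical risk that vaccine-induced T cells could worsen disease after challenge, and protocol 2.2 makes the safety of challenge in vaccinated participants a secondary objective. A comparison of the two arms is the natural way to address it. Protocol 7.2.1 also cites "electrocardiographic (ECG) abnormalities in up to 53% of infected adults, typically with no cardiac symptoms" and says that most of these resolved within 28 days. Changes of that kind could well be judged not clinically relevant and so stay out of the adverse event tables.

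**Working it through.** No sample size, power or event count is in question, so the check follows each sign named in protocol 7.2.6 into the SAP's tables.

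| Sign in protocol 7.2.6 | Category in SAP 3.4.2 | In tables 14.3.4.1 to 14.3.4.4? |
|---|---|---|
| Sinus tachycardia | HR > 100 bpm | Yes |
| Atrioventricular conduction delay | PR > 220 ms | Yes, through the interval |
| Bundle-branch block | QRS > 120 ms | Indirectly |
| ST-segment abnormality | None | No |
| T-wave abnormality | None | No |

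Three of the five named signs reach a table and two do not.

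There are three other places where the two missing signs could be counted.

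1. **Listing 16.2.10.2.** Its title shows that interpretation and morphology are planned data. A listing gives no percentage. It takes in anyone with any abnormal interpretation, so it does not separate changes that are new since the pre-challenge ECG from those already present.
2. **Adverse event tables.** Under protocol 7.2.6 and schedule footnote 6, a change judged clinically relevant or significant becomes an adverse event. SAP 3.1.3 counts treatment-emergent events by preferred term, and SAP 5.4.3 presents tables per treatment by default. These changes are therefore counted by arm.
3. **The table of adverse events of special interest (14.3.1.3).** It counts events reported as such, for example myocarditis itself. It does not count the ECG signs used to look for it.

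What remains uncounted is ST-segment or T-wave change that the investigator does not judge clinically relevant. Protocol 9.1.3 sets no such restriction on the abnormalities to be summarised, and SAP 6.1 does not say that the summary has been narrowed.

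The schedule supports a by-visit table. In the challenge period, ECGs are planned on Day -1, Day 4 and Day 28. SAP 5.2.2 takes the last value before inoculation as the challenge baseline, and SAP 5.2.5 includes unscheduled assessments in the worst case.

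**The case against.** The strongest reply is that the SAP reads protocol 9.1.3 reasonably. The commitment names neither ST-T changes, nor morphology, nor a comparison by arm, and the next sentence names heart rate, PR, QRS and QT. Tables of abnormalities in those variables deliver at least part of it. Clinically relevant ST-T changes reach the adverse event tables, safety analysis is descriptive, and listings are ordered by treatment, so a reader could count by hand among about 134 challenged participants.

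Much of this stands. The commitment is general and is partly met. But the sentence on electronic capture is separate from the one on abnormalities, and 7.2.6 shows that the reader's findings go beyond the captured intervals. A hand count from a listing is not a planned summary.

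A reader might be tempted to go further in four ways, none of which the documents support.

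- **That ST-T changes are never counted by arm.** Those recorded as adverse events are.
- **That adverse event tables miss changes without symptoms.** Protocol 10.1 includes abnormal diagnostic results among adverse events, and 7.2.6 turns on clinical relevance, not symptoms.
- **That a participant with ST-T change is reported as having a normal ECG.** Abnormality is defined per parameter, and no table has an overall normal class.
- **That the 53% in protocol 7.2.1, combined with the 83% attack rate, sizes the omission.** The 53% is an upper figure for any ECG abnormality, given in the discussion of community-acquired influenza. The share that is ST-T change alone is not stated.

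Nor does the earlier presumed myocarditis show that the proposed table would have caught it. Protocol 7.2.1 places that diagnosis 51 days after inoculation and after a further respiratory infection.

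**Conclusion.** The point holds as a reporting gap. No ECG table counts abnormal interpretation or morphology, and two of the five signs named in protocol 7.2.6 have no category. The protocol's percentage with ECG abnormalities is therefore not delivered for ST-segment and T-wave changes that are not recorded as adverse events, and the SAP does not declare this.

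The number of participants affected is unknown. It runs from none, if every such change is recorded as an adverse event or none occurs, up to all participants with an ST-T change. The conclusion rests on two assumptions: that the interpretation and morphology data are collected, as the title of listing 16.2.10.2 indicates, and that some ST-T changes will be judged not clinically relevant, which protocol 7.2.1 makes plausible but does not establish. The gap does not affect the primary endpoint or any clinical rule.

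**What to change.** In SAP 3.4.1, add ECG interpretation and morphology to the available data. In SAP 3.4.3 and the table list, add one table by treatment for challenged participants (the challenge safety set) giving:

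- n (%) with an abnormal ECG interpretation, in the categories actually collected, which the documents do not state;
- n (%) with a treatment-emergent ST-segment or T-wave change.

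Show both at Day 4, at Day 28 and at worst case, relative to the pre-challenge ECG. Tachycardia and conduction delay need no new table, because heart rate, PR and QRS already cover them directly or indirectly. If the sponsor decides against the table, SAP 6.1 should say that the protocol's summary is limited to numeric abnormalities.

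The cost is a little more programming, plus some coding of morphology if it is held as free text. No new assessment is needed.
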